3 STUDY DESIGN

3.1 Characteristics

This is a single center phase 2 open label study starting with a safety lead-in ibrutinib administered as neoadjuvant therapy in patients with localized prostate cancer. We believe that the dose of ibrutinib 840mg x 4 weeks will be well tolerated in patients with localized prostate cancer based on current trial data on ibrutinib but to ensure safety, we will start with a safety run-in. Previously at UCSF, 3 patients were enrolled to the 840 mg/d x 2 weeks dose level. No DLTs were observed. Beginning at WUSM, patients will be enrolled at the dose level of 840 mg/d x 4 weeks. If there are fewer than 2 DLTs, the Phase II dose expansion study will open and enroll up to an additional 18 patients to be treated with ibrutinib 840mg PO daily for 4 weeks.

If there are ≥ 2 DLTs in the safety lead-in, dosing will be de-escalated as follows:

- Level -1: 840 mg/d x 2 weeks, followed by de-escalation if ≥ 2 DLTs to Level -2
- Level -2: 560 mg/d x 2 weeks

In each enrolled patient, neoadjuvant ibrutinib therapy will be followed by radical prostatectomy (RP) performed 7 to 12 days after the last dose of ibrutinib. Pre-treatment and RP tissue will be evaluated for immunologic characterization, Btk expression and pathologic response. The proportion of patients achieving $\geq 50\%$ PSA decline will be assessed. Serum will also be obtained to characterize circulating immune response. All patients will be followed clinically for 4 weeks after RP to monitor for adverse events.

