6.1.3 Other Modalities or Procedures

Blood samples for PSA and for immune assays will be collected at baseline, before RP, and after RP. Radical prostatectomy will be performed at Washington University, at least 7 days but not more than 12 days following the last scheduled dose of ibrutinib (Day 36 to 41; See Table 6.1). Information including WBC count prior to surgery, amount of blood loss during surgery and/or any post-operative complication(s) will be included in the safety analysis. As there is a potential for loss of immune cell infiltration within the prostate tissue after >12 days of not receiving ibrutinib, any patient who undergoes RP after 12 days from the last dose of ibrutinib will be included in the final analysis; however, an additional patient will be accrued as replacement. This will keep the treatment uniform in order to

evaluate for immune response. The maximum number of allowed replacement patients is 4.

Standard institutional practices for the care and treatment of surgical patients will be followed before, during, and after each patient's RP. Patients will be informed in the written consent that radical prostatectomy may be delayed due to adverse events resulting from study treatment, at the discretion of the investigator and performing surgeon.

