6.2 Dose Modifications for an Individual Patient Regardless of Dose Cohort

If a patient experiences any CTCAE v4.0 grade 4 toxicity attributed to treatment, ibrutinib must be discontinued. If a patient experiences any CTCAE v4.0 grade 3 toxicity attributed to treatment, ibrutinib must be held until resolution of the toxicity to grade 1 or the patient's baseline, at which time the patient may resume ibrutinib at 50% of the starting dose. If the patient experiences recurrence of the same grade 3 toxicity while on 50% reduced dose,

ibrutinib must be discontinued. If a grade 3 toxicity does not resolve to grade 1 or the patient's baseline within 2 weeks of holding therapy, ibrutinib must be discontinued.

Ibrutinib Dose Modifications According to Toxicity

Event	Management
Any grade 4 toxicity attributed to treatment	Discontinue ibrutinib
Any grade 3 toxicity attributed to treatment	Hold ibrutinib until \leq grade 1, then resume ibrutinib at 50% starting dose
Recurrence of the same grade 3 toxicity while on half dose	Discontinue ibrutinib
Grade 3 toxicity not resolving to \leq grade 1 within 2 weeks	Discontinue ibrutinib

Clinical judgment of the treating physician should guide the management plan of each patient based on individual benefit/risk assessments.

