Grade 3 (ANC >100,000/mm ³)	Admit patient for close monitoring including CBC and signs and symptoms of leukostasis. Hold ibrutinib until ANC normalizes, at which time resume ibrutinib at 50% of the starting dose.
Grade 4 (clinical manifestations of leukostasis; urgent intervention indicated)	Discontinue ibrutinib. Supportive care including hydration and/or cytoreduction per standard institutional practices.
Other ibrutinib-related AEs	
Grade 1 or 2	Maintain dose level and initiate standard supportive care. If grade 2 toxicity does not improve to ≤ grade 1 with optimal supportive care, reduce ibrutinib dose by 140mg.
Grade 3	Hold ibrutinib until resolve to ≤ grade 1, then reduce dose by 50%.
Grade 4	Discontinue ibrutinib.
Frequency category is based on the following:	

 Very common: anticipated ≥10% Common: anticipated ≥1% and <10% 	
Notes:	

 All dose modifications should be based on the worst preceding toxicity. If a patient requires a dose interruption of >14 days due to a study drug related toxicity, the patient must be discontinued from the study. Patients who discontinue the study for a study related AE must be followed at least once a week for 28 days and subsequently at 28 day intervals until resolution or stabilization of the event, whichever comes first. 	

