8.1.4 Long Term Follow-up Procedures

The study will conclude when all enrolled patients have been followed 4 weeks after RP. All treatment related adverse events will be followed until resolution or stabilization to grade ≤ 2 .

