8.1.5 Discontinuation of Therapy

The Investigator will withdraw a patient whenever continued participation is no longer in the patient's best interests. Reasons for withdrawing a patient include, but are not limited to, disease progression, the occurrence of an adverse event or a concurrent illness, a patient's request to end participation, a patient's non-compliance or simply significant uncertainty on the part of the investigator that continued participation is prudent. There may also be administrative reasons to terminate participation, such as concern about a patient's compliance with the prescribed treatment regimen.

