8.3 Usage of Concurrent/Concomitant Medications

Supportive medications in accordance with standard practice (such as for emesis, diarrhea, etc.) are permitted. Use of neutrophil growth factors (filgrastim and pegfilgrastim) or red blood cell growth factors (erythropoietin) is permitted per institutional policy and in accordance with the ASCO guidelines ([Smith 2006](#)). Transfusions may be given in accordance with institutional policy.

Short courses (≤ 14 days) of steroid treatment for non-cancer related medical reasons (e.g., joint inflammation, asthma exacerbation, rash, antiemetic use and infusion reactions) at doses that do not exceed 100 mg per day of prednisone or equivalent are permitted.

Treatment for autoimmune cytopenias are permitted for <14 days at doses that do not exceed 100 mg per day of prednisone or equivalent.

Concomitant use of ibrutinib and drugs that inhibit or induce CYP3A should be recorded on the CRF. Use of medications that inhibit platelet function and may increase the risk of bleeding (e.g. Aspirin) should be recorded on the CRF. Use of any medications that may have immunosuppressive effects should be recorded on the CFR.

All AEs and serious AEs (SAEs) that occur on study drug or within 30 days after the last dose of study drug, will be recorded on case report forms (CRFs) from enrollment through 4 weeks post-surgery.

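### The Section 6.3 table note takes a man with a drug-related hold of more than 14 days off the study, where Section 6.2 stops only ibrutinib and the plan needs his surgical tissue and follow-up

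*Combined protocol and SAP*

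**What the plan says.** The general notes to the toxicity table in Section 6.3 contain two linked rules. The first is "If a patient requires a dose interruption of >14 days due to a study drug related toxicity, the patient must be discontinued from the study". The second is "Patients who discontinue the study for a study related AE must be followed at least once a week for 28 days", and then every 28 days until the event resolves or stabilizes. Neither mentions tissue, research blood, PSA or the post-operative visit.

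Section 6.2 covers the grade 3 case of the same event. If the toxicity has not come down to grade 1 or baseline "within 2 weeks of holding therapy, ibrutinib must be discontinued". Its table gives the same instruction.

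Elsewhere the plan expects a full course of data from each man:

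- Section 3.1 has prostatectomy follow treatment in each enrolled patient, and adds: "All patients will be followed clinically for 4 weeks after RP to monitor for adverse events".
- Section 8.1.4: "The study will conclude when all enrolled patients have been followed 4 weeks after RP".
- Section 8.3 has adverse events recorded "from enrollment through 4 weeks post-surgery".
- Appendix 3 collects paired tissue from all patients.
- Sections 12.4 and 12.6.1 analyze every dosed patient for efficacy as well as safety. Section 12.4 does not replace men removed for treatment-related toxicity.
- Section 6.1.3 keeps late surgeries in: "any patient who undergoes RP after 12 days from the last dose of ibrutinib will be included in the final analysis".

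**The concern.** For a grade 3 toxicity, two weeks of holding under Section 6.2 and more than 14 days of interruption under Section 6.3 describe practically the same clinical situation. One rule ends the drug; the other ends study participation. Both are mandatory.

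The primary activity endpoint is a change from biopsy to prostatectomy specimen, so a man taken off study before surgery may give no endpoint. He nevertheless stays in the efficacy population and is not replaced. His post-operative PSA and immune blood, and the surgical information that Section 6.1.3 brings into the safety analysis, could go with him. Such losses would not be random: they would fall on men whose toxicity was slow to resolve, in a trial with safety around surgery among its primary aims.

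**Working it through.** **Step 1: the provisions side by side**

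| Situation | Section | Disposition |
|---|---|---|
| Grade 3, unresolved after 2 weeks of hold | 6.2, text and table | Stop ibrutinib |
| Drug-related interruption of more than 14 days | 6.3, note | Leave the study; adverse event follow-up |
| Grade 4 toxicity | 6.2; 6.3 table | Stop ibrutinib |
| DLT in the lead-in | 6.1.4 | May leave protocol therapy and have surgery at the surgeon's discretion |
| Prohibited medication taken | 8.5 | Remain on study |
| Removed from study for toxicity | 3.5, 12.4 | Follow treatment-related events to grade 2 or lower |

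Read literally, a man with a grade 4 event stops only the drug, while a man with a long hold for a lesser event leaves the study. The 6.3 table also holds drug for grade 2 anemia, thrombocytopenia and neutropenia, so a slow grade 2 recovery could trigger the note. Section 6.2 does not address those holds. No section says whether a man removed under the note still provides prostatectomy tissue, later blood and PSA, or the post-operative visit.

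**Step 2: how many men could be affected**

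Dosing runs from day 1 to day 28 (Sections 6.1.2 and 8.2). A hold that exceeds 14 days within that period must begin by day 14: days 14 to 28 inclusive are 28 − 14 + 1 = 15 days. The documents give no rate of such holds. The pooled 9.4% discontinuation for adverse events in Section 1.2.2 comes from B-cell malignancies with a median of 5.1 months on drug; it is not a rate of holds over 14 days, so I do not use it. I assume 0, 1 or 2 men lost.

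**Step 3: effect on power**

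Inputs from Section 12.3: 24 evaluable men, null rate 5%, target rate 20%, one-sided exact binomial test, success at 4 responders (my reading of the last sentence of its first paragraph).

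Formula: P(X ≥ 4) = 1 − Σ C(n,k) p^k (1−p)^(n−k), summed over k = 0 to 3.

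The plan's own figures first. For n = 24 and p = 0.20 the four terms are 0.0047, 0.0283, 0.0815 and 0.1493. They sum to 0.2639 (unrounded terms), so power is 0.736. At p = 0.05 the same rule gives a one-sided level of 0.030. The stated 0.818 and 0.044 are not reproduced at n = 24; they are the values for n = 27 (0.8177 and 0.0437). That discrepancy is independent of the note, and I use 0.736 as the base here.

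| Men lost (assumed) | Evaluable | Power at 20% | Level at 5% |
|---|---|---|---|
| 0 | 24 | 0.736 | 0.030 |
| 1 | 23 | 0.703 | 0.026 |
| 2 | 22 | 0.668 | 0.022 |

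Each lost specimen costs 3 to 4 percentage points, provided the lost man would have responded with probability 20%. If short exposure makes him a non-responder anyway, losing his specimen does not change the chance of reaching four responders.

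**The case against.** The best defense is that the note is loosely worded and means off treatment. Section 8.1.5 is headed as discontinuation of therapy, yet its text says "The Investigator will withdraw a patient whenever continued participation is no longer in the patient's best interests", so the protocol uses the two ideas interchangeably. The second 6.3 note keeps men under observation after they leave the study, so leaving cannot mean the end of all contact. Section 6.1.4 lets a man with a DLT come off protocol therapy and still have surgery. Strictly, Sections 6.2 and 6.3 can both be obeyed, because 6.2 never says that the man stays on study. Surgery is each man's planned curative treatment, so a specimen would probably exist in any case.

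Much of this stands. It makes off treatment a plausible intention and limits the number of men at risk. In the six-man lead-in, attributable grade 3 and 4 events are DLTs (asymptomatic lymphocytosis aside), so the surgical provision in 6.1.4 already reaches those men. That leaves mainly the 18 later men, plus slow grade 2 cytopenias in the lead-in.

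It does not remove the ambiguity. The note is mandatory, names the study rather than the drug, and sits under a table that names the drug when it means the drug. A specimen taken in routine care is not the same as a specimen the trial is instructed to collect from a man no longer on study.

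A reader might infer that men removed under the note go without safety follow-up. The documents do not support that: Sections 3.5, 6.3 and 12.4 all require treatment-related events to be followed. What is left unstated is endpoint data and the post-operative visit.

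**Conclusion.** The inconsistency is in the text and worth correcting, but it is minor. The note may well mean off treatment; it does not say so, and its literal reading conflicts with what the plan expects of every dosed man. The effect ranges from none to a power of 0.668 against 0.736, under an assumed loss of 0 to 2 men, the four-responder rule, and a 20% response probability in the men lost.

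Two stronger conclusions are tempting and unsupported. One is that the note will certainly remove primary-endpoint tissue: no section says tissue will not be collected, and several suggest it would be. The other is that the shortfall from the stated power of 0.818 is due to this rule: it is present with all 24 men evaluable and belongs to the sample size calculation.

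**What to change.** In the two Section 6.3 notes, name ibrutinib instead of the study: the man is *discontinued from ibrutinib*, and the follow-up note applies to those who *discontinue ibrutinib*. Add one sentence there, and beside the removal wording in Sections 3.5 and 12.4:

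*Men who stop ibrutinib for toxicity stay on study for end-of-therapy blood and PSA, AE follow-up and, if RP is performed, RP tissue, the RP Form and the 4-week post-RP visit, unless they withdraw consent.*

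The condition on surgery is needed because the operation may not go ahead for medical reasons, and Section 6.1.4 leaves it to the surgeon after a DLT.

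The cost is a few words and one repeated sentence. No visit, dosing rule or sample size changes, since a man under the note already stops the drug. The downside is that a few men with short exposure, often more than 12 days off drug at surgery, contribute to the primary proportion. Section 12.4 already requires that.

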7 REGULATORY AND REPORTING REQUIREMENTS

The entities providing oversight of safety and compliance with the protocol require reporting as outline below. Please refer to Appendix 5 for definitions and Appendix 6 for a grid of reporting timelines.

Adverse events will be tracked from the start of study treatment through 30 days after the end of treatment. All adverse events must be recorded on the toxicity tracking case report form (CRF) with the exception of:

- Baseline adverse events, which shall be recorded on the medical history CRF
- Adverse events related to prostatectomy

Refer to the data submission schedule in Section 11 for instructions on the collection of AEs in

the EDC.

Reporting requirements for Washington University study team may be found in Section 7.1.

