2 OBJECTIVES AND ENDPOINTS OF THE STUDY

2.1 Objectives

2.1.1 Primary Objectives

1. To assess safety in patients with localized prostate cancer.
2. To characterize B and T cell infiltration within prostate tissue of men with localized prostate cancer treated with neoadjuvant ibrutinib, and to compare B and T cell infiltration to a reference population of untreated patients who underwent RP.

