6.1.4 Dose Limiting Toxicities

Each patient in the safety lead-in will be assessed periodically for the development of any toxicity as outlined in Section 7 Study Procedures and Observations. Toxicity will be assessed according to the NCI CTCAE v4.0. Dose adjustments will be made according to the system showing the greatest degree of toxicity.

Dose de-escalation in this study will be based on the occurrence of dose-limiting toxicities (DLTs) that occur during the duration of ibrutinib therapy and the period after the last dose of ibrutinib until the day of surgery. DLTs will be defined as any of the following that are attributable to ibrutinib.

- Any grade 4 toxicity, including hematologic toxicities with the exception of lymphocytosis. Lymphocytosis, in the absence of clinical symptoms, is excluded from DLT, as this may be considered an on-target pharmacodynamics effect of BTK inhibition.
- Any grade 3 toxicity.
- Any recurrence of the same grade 3 toxicity.
- Any delay of RP due to study-drug related toxicity.
- Any complications of RP (e.g., bleeding, delayed wound healing) deemed to be related to study drug.

The dose of study drug should be modified according to the dose modification guidelines, including any of the following toxicities:

- Grade 4 ANC (<500/mm³) for more than 7 days.
- Grade 3 thrombocytopenia (<50,000/mm³) in the presence of clinically significant bleeding events.
- Grade 4 thrombocytopenia (<25,000/mm³).
- Grade 3 or 4 nausea, vomiting, or diarrhea if persistent, despite optimal anti-emetic and/or anti-diarrheal therapy.

Patients who experience a DLT may be removed from protocol therapy and undergo RP at the discretion of the operating surgeon.

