11.1 Adverse Event Collection in the Case Report Forms

All adverse events that occur beginning with start of treatment (minus exceptions defined in Section 7.0) must be captured in the Toxicity Form. Baseline AEs should be captured on the Medical History Form.

Participant death due to disease progression should be reported on the Toxicity Form as grade 5 disease progression. If death is due to an AE (e.g. cardiac disorders: cardiac arrest), report as a grade 5 event under that AE. Participant death must also be recorded on the Death Form.

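### Section 7 keeps prostatectomy-related adverse events off the Toxicity Form and names no other form for them, contradicting Sections 6.1.3 and 8.3

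*Combined protocol and SAP*

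**What the plan says.** Safety is the first primary objective (Section 2.1.1): "To assess safety in patients with localized prostate cancer".

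Section 7 sets the recording rule: "All adverse events must be recorded on the toxicity tracking case report form (CRF) with the exception of" two classes of event. The first is "Baseline adverse events, which shall be recorded on the medical history CRF". The second is "Adverse events related to prostatectomy", with no form named. Section 11.1 repeats the exclusion: adverse events from the start of treatment ("minus exceptions defined in Section 7.0) must be captured in the Toxicity Form").

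Three other places point the other way:

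- Section 6.1.3, on surgery: "amount of blood loss during surgery and/or any post-operative complication(s) will be included in the safety analysis".
- Section 8.3, and the abstract in the same words: adverse events and SAEs on study drug or within 30 days of the last dose "will be recorded on case report forms (CRFs) from enrollment through 4 weeks post-surgery". There is no prostatectomy exception.
- Section 6.1.4 lists among the dose-limiting toxicities "Any complications of RP (e.g., bleeding, delayed wound healing) deemed to be related to study drug".

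**The concern.** Neoadjuvant dosing raises a safety question of its own: does the drug make surgery worse? The protocol warns of bleeding with invasive procedures (Sections 1.2.2.1, 8.3.1 and 8.7). Section 7 nevertheless filters by cause before anything is written on the main safety form.

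One event can be related both to prostatectomy and to ibrutinib; a post-operative bleed is the obvious case. The protocol does not say who decides which label applies, or what happens when both do. If a site reads the exception at face value, a mixed-cause event may never reach the Toxicity Form, and the drug's contribution could be hard to assess later. Any resulting error in that form runs towards fewer recorded events.

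**Working it through.** The plan states no figure on this point, so the check is a cross-reading followed by day arithmetic.

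**1. Where each kind of perioperative event goes under the current text**

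| Event | Route other than the Toxicity Form |
|---|---|
| Any serious event | Report to the drug supplier (7.1.3); a MedWatch form is in the Section 11 schedule |
| Bleeding of grade 3 or higher, serious bleeding of any grade, or CNS bleeding of any grade | Event of special interest, reported to the supplier (7.1.3.3 and the major hemorrhage definition); bleeds needing red-cell transfusion are to be graded 3 or higher |
| Blood loss during surgery | Possibly the RP Form (Section 11), due at the time of surgery; its content is not described |
| Non-serious wound complication after surgery | None named |
| Non-serious, non-CNS bleeding below grade 3 after surgery | None named |

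Two further provisions do not fill the last two rows. The follow-up visit (Section 8.1.3, Day 64) includes an adverse-event evaluation, but Section 11.1 still keeps exempt events off the Toxicity Form. Section 7.2 requires EDC capture of events that need no expedited report, but the four types it lists do not include prostatectomy events.

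**2. Whether the analysis makes up for it**

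Section 9.2 lists the safety data as adverse events, examinations, vital signs, performance status and laboratory results. Section 12.6.2.1 summarises SAEs and non-SAEs descriptively. Neither specifies an output for blood loss or post-operative complications, although Section 6.1.3 commits to including them.

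**3. The recording window**

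Inputs: last dose on Day 28 (6.1.2), tracking to 30 days after treatment (Section 7), prostatectomy on Day 36 to 41 (6.1.3), and 4 weeks = 28 days of follow-up (3.5).

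- Section 7 window closes: 28 + 30 = Day 58.
- Four weeks after surgery: 36 + 28 = Day 64, to 41 + 28 = Day 69.
- Post-operative days inside the window: 58 − 36 = 22, to 58 − 41 = 17.
- Post-operative days outside it: 28 − 22 = 6, to 28 − 17 = 11.

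So even a non-exempt event is covered by Section 7 for only 17 to 22 of the 28 days. Section 8.3 does not settle this, because its one sentence carries both the 30-day limit and the 4-week end point.

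**4. The DLT window**

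Section 6.1.4 counts DLTs up to the day of surgery, and the abstract says the period before prostatectomy. The same section lists complications of prostatectomy as a DLT criterion and gives delayed wound healing as an example, which would ordinarily appear after that day. This conflict exists whatever Section 7 says.

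**The case against.** The strongest reply is that Section 7 exempts these events from one form, not from recording. Section 8.3 and the abstract require CRF recording; serious events and major hemorrhage have a reporting route with no prostatectomy exception; adverse events are evaluated at Day 64; and an RP Form exists. Read alongside Section 6.1.4, the exception can be taken to mean purely surgical events, which leaves drug-attributed complications recordable.

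Much of this stands, and it rules out three stronger readings that a reader might infer.

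- *That perioperative events are not recorded at all.* The routes above contradict this for serious events and major bleeding. The RP Form's content is unknown, so one cannot say what it omits; one can say only that later complications are not clearly covered by a form due at the time of surgery.
- *That nearly every post-operative complication would be filtered out.* Nothing in the documents supports that share. It depends on an attribution step that the plan leaves undefined.
- *That the exemption undermines the lead-in's decision on 2 DLTs among 6 patients.* The DLT window ends on the day of surgery, so later complications fall outside it regardless of Section 7. The criterion also counts only drug-attributed complications, so the chance of a complication of any cause is not comparable with that threshold.

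What the reply does not remove is the contradiction between sections, the absence of a named form for the remaining events, and the silence on mixed causes. The benign reading of the exception is possible, but the text does not state it.

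**Conclusion.** The point holds as an internal contradiction with a specific gap in data capture. Sections 7 and 11.1 cannot be reconciled with Section 6.1.3, or with Section 8.3 and the abstract, as written. The events exposed are non-serious post-operative events that are not events of special interest, chiefly wound complications and lower-grade bleeding. They are likely to be missed or captured inconsistently, so the Toxicity Form, and safety summaries drawn from it, can understate perioperative toxicity on a primary objective.

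The number of events cannot be estimated, because the documents give neither a complication rate nor an attribution rule. The only firm figure is the window: 6 to 11 of the 28 post-operative days lie outside Section 7's tracking period. It assumes the last dose is on Day 28 and surgery falls within the planned days; later surgery or an earlier last dose would widen it. The conclusion also assumes that sites follow Section 7 literally and that the RP Form is not updated after surgery.

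**What to change.** - Delete the prostatectomy exception in Section 7 and its carry-over in Section 11.1.
- Record post-operative events on the Toxicity Form, graded, with separate attributions to ibrutinib and to surgery, so that both can be marked for one event.
- Add to Section 12.6.2.1 a descriptive table of blood loss and post-operative complications regardless of attribution, which delivers what Section 6.1.3 already promises.
- State one end date for adverse-event recording and use it in the abstract and in Sections 7 and 8.3.
- Separately, reconcile the Section 6.1.4 DLT window with its prostatectomy-complication criterion. That choice belongs to the sponsor and the investigator.

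The cost is protocol wording, a second attribution field on an existing form and one extra table. The downside is more expected surgical events on the adverse-event listing, which the separate attributions keep interpretable. It is best done before further data accrue, since attribution not recorded at the time is hard to reconstruct. The recording changes alter no dose, treatment rule or DLT definition.
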